3.8. Subgroups

To assess the consistency in treatment effects across difference subgroup levels, subgroup analyses may be explored for efficacy endpoints, such as VOE-CR and sVOE-CR. Subgroup analyses will include, but may not be limited to, age group (adolescents [≥ 12 and < 18 years old at Informed Consent] versus adults [≥ 18 years old at Informed Consent]), sex, race, alpha-globin genotype, and/or stroke history (Yes/No).

3.9. Withdrawals, Dropouts and Lost to Follow-Up

Subjects withdrawn from the study prior to drug product infusion may be replaced. Subjects who receive drug product but subsequently withdraw will not be replaced.

For subjects who withdraw for reasons other than withdrawal of consent, any SAEs open at the time of discontinuation should be followed up until resolution or are determined to be a stable or chronic condition.

If withdrawal is before drug product infusion, subjects should remain on study for at least 30 days after any invasive study procedure (e.g., mobilization, liver biopsy) before withdrawal. In the rare case a subject undergoes myeloablation and receives back-up cells instead of drug product, subject should remain on the study for at least 3 months post myeloablation.

If withdrawal is after drug product infusion, subjects will be asked to complete the same assessments as specified in the SOE for Month 24 (Early Termination Visit assessments) and will be asked to enroll in the long-term follow-up study.

3.10. Missing Data

The imputation rules for missing data can be found in [Appendix 6.1, Table 11](#).

3.11. Analysis Visit Windows

All evaluation visits are expected to occur following scheduled evaluation per the protocol. The data used in summaries will be tabulated per the evaluation visit as recorded on the CRF. If the evaluation visit is missing due to early withdrawal or missing visits but there is data from unscheduled or additional visit that is inside an analysis visit window as defined in [Appendix 6.2, Table 12](#), then the data from the unscheduled or additional visit will be used for the analysis visit window in data summaries.

For endpoints that are not Hb fractions, if subjects have multiple unscheduled or additional evaluations within an analysis visit window, the evaluation closest to the target visit date will be used in the summary tabulations. In case of evaluations equidistant to the target visit date within an analysis visit window, results of the earlier evaluation will be used. This applies to all assessments without designated visits.

For Hb fractions, if subjects have multiple unscheduled or additional evaluations within an analysis visit window, the mean of these evaluations will be used in the summary tabulations and the detailed rules can be found in [Section 4.4](#).

Windows for time course distributions of AEs and concomitant medications are based on the following time periods:

- ICF until prior to either initiation of mobilization or bone marrow harvest (ICF to < MB)
- Initiation of mobilization (or bone marrow harvest) until prior to initiation of conditioning (MB to < C)
- Initiation of conditioning until prior to initiation of neutrophil engraftment (NE) (C to < NE)
- Initiation of NE through Month 24 (NE to M24)
- Day 1 (drug product infusion) until prior to initiation of NE (D1 to <NE)
- Day 1 (drug product infusion) through Month 24 (D1 to M24)
- Informed Consent Form through Month 24 (ICF to M24)

Note: initiation of NE is counted as the first date of the 3 consecutive ANC assessments that are $\geq 0.5 \times 10^9/L$ obtained on different days after the initial post-transplant nadir by Day 43.

Windows for time course distributions of clinical laboratory shift tables (shift categories defined by CTCAE grade, Version 4.03) are based on the following time periods:

- Initiation of mobilization (or bone marrow harvest) until prior to initiation of conditioning (MB to < C)
- Initiation of conditioning until prior to initiation of NE (C to < NE)
- Initiation of NE through Month 12 (i.e., Day 365) (NE to M12)
- >Month 12 (i.e., Day 366) through Month 24 (>M12 to M24)
- Day 1 (drug product infusion) until prior to initiation of NE (D1 to <NE)
- Day 1 (drug product infusion) through Month 24 (D1 to M24)

3.12. Interim Analyses

Interim analyses are planned in support of regulatory submissions. The timing of these analyses and the number of subjects included in each analysis will take into account input from regulatory agencies and applicable regulatory guidance. The rationale for each analysis will be documented outside of this SAP.

The summary tables for interim analysis will be presented based on all data available as of the data cut-off, except for these efficacy endpoints specified below. Only evaluable subjects will be included in summary tables:

- **VOE-CR, sVOE-CR, and change in annualized number of VOEs or sVOEs in the 6 to 18 months post-drug product infusion:** only include Group C subjects in the TPVOE who have or would have at least 18 months follow up post-drug product infusion.
- **sVOE-CR24, VOE-CR24, sVOE-75 and change in annualized number of VOEs or sVOEs in the 24 months post-drug product infusion:** only include Group C subjects in TPVOE who have Month 24 visit or would have at least 24 months follow-up post-drug product infusion.
- **Globin Response (GR):** only include subjects in TP who achieve Globin Response, have or would have at least 18 months follow up post-drug product infusion.
- **Globin Response at Month 24:** only include subjects in TP who achieve Globin Response and either (1) have Month 24 HPLC visit assessment or (2) would have at least 24 months follow up post-drug product infusion.
- **pRBC transfusions, and hospitalizations endpoint:** only include Group C subjects in the TP who have or would have at least 18 months of follow-up post-drug product infusion.

For Group A and B, the analysis population for interim analysis will be based on the same criteria as the criteria of interim analysis for Group C.

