4.4. Efficacy Analysis

The analysis populations for the efficacy endpoints identified below can be found in [Table 3](#). Listings will be provided for all efficacy endpoints. Supportive figures will be provided as needed.

The definitions of investigator VOEs, protocol VOEs, adjudicated VOEs, protocol sVOEs, and adjudicated sVOEs are listed in [Appendix 6.4, Table 14](#). All sVOE or VOE-related efficacy endpoints will be based on adjudicated sVOEs or adjudicated VOEs among Group C subjects in the TPVOE, with a 95% CI estimated for applicable binary endpoints; Supplementary analyses may also be performed based on protocol sVOEs, protocol VOEs or investigator VOEs. The endpoints will also be presented for Groups A and B subjects in the TPVOE without 95% CI estimated for the binary outcomes.

For Hb fraction analysis, the globin sample (within the analysis visit window) and the hematology sample will be merged by date. If the dates match, this Hb will be selected, even if a transfusion occurs on the same date. If a globin sample exists but there is no corresponding hematology sample with the same date, then the globin sample will be merged with the closest Hb result with no transfusion between the globin and hematology sample. If there are multiple Hb records on the same date, the one with the lowest value will be used. If the selected Hb is not within a ± 7 day window of the globin sample, the fraction will be footnoted in the data listings. An analysis visit window will be applied for by visit summary tables and figures (see [Appendix 6.2, Table 12](#) for analysis visit window). If there are multiple fractions for a subject within a given analysis visit window, an average of the fractions and Hb used to derive the fractions will be calculated and included in summary tables and figures.

The estimands for the primary and key secondary efficacy endpoints can be found in [Table 4](#).

Table 4. Estimands for Primary and Key Secondary Efficacy Endpoints

	Primary Efficacy Estimand	Key Secondary Efficacy Estimand	Key Secondary Efficacy Estimand
Treatment	bb1111	bb1111	bb1111
Population	Group C subjects in TPVOE (Group C evaluable subjects in TPVOE- for interim analysis)	Group C subjects in TPVOE (Group C evaluable subjects in TPVOE- for interim analysis)	Group C subjects in TP (Group C evaluable subjects in TP- for interim analysis)

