Endpoint (variable)	Complete resolution of adjudicated VOEs between 6 months and 18 months after drug product infusion (i.e., VOE-CR)	Complete resolution of adjudicated severe VOEs between 6 months and 18 months after drug product infusion (i.e., sVOE-CR)	Globin Response, as defined in Section 1.2.6.2
Intercurrent event (ICE)	Discontinues from the study before reaching the 18th month follow-up post-drug product infusion will be considered as a non-responder.	Discontinues from the study before reaching the 18th month follow-up post-drug product infusion will be considered as a non-responder.	Discontinues from the study before achieving Globin Response will be considered as a non-responder. pRBC transfusion is considered an intercurrent event. Starting \geq 60 days after last pRBC transfusion, a subject should meet Globin Response for a continuous period of at least 6 months after drug product infusion.
Population-level Summary	Proportion of subjects achieving VOE-CR among the subjects who are in the analysis population	Proportion of subjects achieving sVOE-CR among the subjects who are in the analysis population	Proportion of subjects achieving Globin Response among subjects who are in the analysis population

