A TP subject will be considered as a non-responder if the subject does not achieve Globin Response before discontinuing from the study.

The percentage of subjects who achieve Globin Response will be presented with a 2-sided exact 95% CI using the Clopper-Pearson method for the binomial distribution. The success criterion at

the final analysis will be at least 24 out of 41 subjects achieving Globin Response (i.e., rate of Globin Response $\geq 59\%$), giving a lower bound of the 95% CI greater than 40%, if exactly 41 TP subjects in Group C. If there are fewer than 41 subjects in the analysis population, with the same assumptions such as the null hypothesis as 40% and alternative hypothesis as 70%, the power and success criterion can be found in [Appendix 6.3, Table 13](#).

Analysis for Groups A and B

The number and percentage of subjects reaching Globin Response will be reported by group for Groups A and B subjects in TP at final analysis.

No 95% CI will be presented given the relatively small sample size.

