4.4.3. Analysis of Other Efficacy Endpoints

4.4.3.1. Characterization of Globin Response (only for Group C subjects who have achieved Globin Response)

- Proportion of subjects who meet the definition of Globin Response at Month 24**
 - The numerator is the number of subjects who continuously meet Globin Response criteria from the first date of Globin Response initiating (t_0) to Month 24 visit of HPLC assessment
 - The denominator is the number of subjects who have achieved Globin Response.

If after achieving Globin Response, a subject discontinues from the study before having the Month 24 visit of HPLC assessment, then the subject will also be considered as a non-responder.

The percentage of subjects who maintain Globin Response at Month 24 will be presented with a 2-sided 95% CI using Clopper-Pearson method.

Supplementary Analyses

The following Supplementary analyses will be conducted:

Analysis Population	Supplementary Analysis
TP	
The primary analysis will be repeated, but after achieving Globin Response, subjects with death or discontinuation unrelated to the drug product will be considered as not evaluable.
 
If after achieving Globin Response but before having the Month 24 visit of HPLC assessment, there is death or discontinuation related to the drug product, then the subject will be considered as a non-responder.

- Duration of Globin Response**

Duration of Globin Response is from the first date of Globin Response initiating (t_0) to the date of last HPLC assessment such that the weighted average of HbA^{T87Q} percentage of non-transfused total Hb, non-transfused total Hb, and non-transfused total Hb increase from the baseline total Hb (if baseline total Hb is available) continuously meet Globin Response criteria

during this time period. Duration of Globin Response (in months) and these weighted average values during Globin Response will be summarized.

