5.2. Changes from Previous SAP (Version 2.0)

Section Number	Section	Changes
4.4.1	Analysis of Primary Efficacy Endpoint	
Clarified that only the supplementary analyses for Group C subjects based on the protocol VOEs and the investigator VOEs in TPVOE will be performed for the final CSR.
 
Removed the supplementary analysis in the ITT population with ≥ 4 protocol VOEs in the 24 months prior to Informed Consent. The analysis was performed for the interim CSR, in case the agency wanted the analysis based on the ITT population. The result was however not of the agency's interest. Moreover, this analysis was heavily weighted by subjects who discontinued prior to receiving the benefit of treatment.

4.4.2.1	Adjudicated sVOE-CR	
Clarified that only the supplementary analysis for Group C subjects based on the protocol sVOEs in TPVOE will be performed for the final CSR.
 
Removed the supplementary analysis in the ITT population with ≥ 4 protocol VOEs in the 24 months prior to Informed Consent. See the change above made in Section 4.4.1 for the rationale.

4.4.2.2	Globin Response	Removed the imputation rules of missing HPLC assessments due to COVID-19 pandemic. The imputation rules were never implemented, because of no such cases in data by the end of the pandemic.

Section Number	Section	Changes
		Removed the supplementary analysis in the ITT population with ≥ 4 protocol VOEs in the 24 months prior to Informed Consent. See the change above made in Section 4.4.1 for the rationale.
4.4.3.1	Characterization of Globin Response	Added a supplementary analysis. In the definition, added “After achieving Globin Response, subjects with death or discontinuation unrelated to the drug product will be considered as not evaluable.” This is to exclude the subject who discontinued due to sudden death which was unrelated to the drug product, according to communication with the agency.
4.4.3.2	Hematologic Endpoints	Removed “starting from Month 1 post-drug product infusion”.
4.4.4	Analysis of Exploratory Efficacy Endpoints	Added the analyses of bone marrow smear.
4.4.5	Analysis of Correlation	Added the correlation between HbAT87Q vs. HbS (% of non-transfused total Hb) at Month 6
4.5	Pharmacodynamic Analysis and Correlation Analysis	Deleted the spaghetti plots of PB %LVV+ and AUC of sickled RBCs, and the correlation analyses related to the two parameters.
4.6.1	Adverse Events	Added AE/SAE attributed to SCD post Month 6

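### SAP 3.12 makes having achieved Globin Response a condition for entering the interim Globin Response denominator, so the interim rate is either 100% by construction or biased upward

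*SAP*

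**What the plan says.** SAP 3.12 says of the listed efficacy endpoints at an interim: "Only evaluable subjects will be included in summary tables". It then defines evaluability endpoint by endpoint.

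- **VOE-CR and sVOE-CR:** Group C subjects in TPVOE with actual or potential follow-up of 18 months. There is no condition on outcome.
- **Transfusions and hospitalizations:** the same follow-up rule, in Group C subjects of the TP.
- **Globin Response:** "only include subjects in TP who achieve Globin Response, have or would have at least 18 months follow up post-drug product infusion".
- **Month 24 Globin Response:** responders only, joined to the follow-up condition by an explicit 'and either (1) or (2)'.

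SAP Table 4 makes the evaluable set the analysis population for Globin Response: "Group C subjects in TP (Group C evaluable subjects in TP- for interim analysis". It summarises the endpoint as the proportion of that population who respond. Its intercurrent-event row says: "Discontinues from the study before achieving Globin Response will be considered as a non-responder". SAP 4.4.2.2 repeats the rule: "A TP subject will be considered as a non-responder if the subject does not achieve Globin Response before discontinuing from the study".

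A responders-only denominator is stated as intended for one endpoint, maintenance of response at Month 24 (SAP 4.4.3.1): "The denominator is the number of subjects who have achieved Globin Response". Neither document states it for Globin Response itself. Protocol 7.4.4.2.2 and SAP Table 3 both use Group C subjects in the TP.

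**The concern.** A response rate needs a denominator fixed without reference to response. The Globin Response bullet breaks that rule, while the VOE-CR and transfusion bullets beside it do not.

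The bullet has no conjunction after its comma, so it can be read two ways. If both conditions apply, the set holds only responders. The rule that counts early discontinuers as non-responders then cannot operate, because such a subject never enters. If the comma means 'or', subjects with 18 months of follow-up enter regardless of outcome, but those with less enter only if they have already responded. Subjects still waiting to respond are left out.

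SAP 3.12 says the interims support regulatory submissions, and SAP 5.2 shows that one interim report exists; of a since-removed supplementary analysis it says "The analysis was performed for the interim CSR". The change list in SAP 5.2 shows no edit to 3.12. The documents do not show which denominator that report used for Globin Response.

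**Working it through.** **The plan's own figure first.** Inputs from SAP 3.1: n = 41, null 40%, alternative 70%, one-sided alpha 0.025, exact binomial test.

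- P(Bin(41, 0.4) ≥ 23) = 0.0270, above 0.025.
- P(Bin(41, 0.4) ≥ 24) = 0.0126, so 24 is the right cut-off.
- P(Bin(41, 0.7) ≥ 24) = 0.9586, matching the stated 96%.

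The final-analysis design is sound.

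**Reading 1: both conditions required.** With r responders in the set, the rate is r/r = 100% for any true rate. The exact p-value against 40% is 0.4^r. Four of four gives 0.0256 and five of five gives 0.0102, so five responders would pass.

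**Reading 2: comma means 'or'.** Let n18 be the subjects with 18 months or more (actual or potential), X the responders among them, and Y the subjects under 18 months who have already responded. The interim rate is (X + Y)/(n18 + Y). This is never below X/n18, and it is strictly above it when Y > 0 and X < n18. Globin Response needs about 6 continuous months starting at least 60 days after the last transfusion (SAP 4.4.2.2), so it can be met well before Month 18 and Y > 0 is to be expected when follow-up is incomplete.

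*Inputs.* 36 Group C subjects infused (SAP Table 1) and a true rate of 40%. Two quantities are not in the documents and are assumed: the split at 18 months, and the share f of eventual responses among the under-18-month subjects already met at the cut-off.

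*Model.* X ~ Bin(n18, 0.4) and Y ~ Bin(36 − n18, 0.4f). The expected rate is the exact mean of (X + Y)/(n18 + Y). The nominal type I error is P(X + Y ≥ c), where c is the smallest value with P(Bin(n18 + Y, 0.4) ≥ c) ≤ 0.025.

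*Check by expected counts*, 20/16 split, f = 1: (8 + 6.4)/(20 + 6.4) = 54.5%. The exact mean is 54.3%.

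| Split (≥18 / <18 months) | Expected rate, f = 1, 1/2, 1/4 | Nominal type I error, f = 1, 1/2, 1/4 |
|---|---|---|
| 20 / 16 | 54%, 48%, 44% | 0.258, 0.091, 0.044 |
| 25 / 11 | 49%, 45%, 42% | 0.120, 0.053, 0.032 |
| 30 / 6 | 44%, 42%, 41% | 0.051, 0.031, 0.024 |
| 36 / 0 | 40% | 0.020 (cut-off 21 of 36) |

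The f = 1 values are ceilings, because recently infused subjects cannot yet have met a 6-month criterion. At that ceiling the nominal error is 0.024 with 2 of 36 under 18 months and 0.029 with 3, so 3 is where 0.025 is first exceeded. At the design rate of 70% the ceiling expected rates are 81%, 77% and 74% for the three splits.

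**Follow-up-only entry.** The expected rate equals the true rate. The exact type I error is 0.021, 0.013 and 0.021 for n = 20, 25 and 30, all below 0.025.

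**The case against.** The strongest reply is that the 100% reading is not what the authors meant. The bullet contains no 'and', whereas the Month 24 bullet next to it uses one. Table 4 asks for the proportion of responders within the analysis population, which is empty of meaning if everyone in it is a responder. The discontinuation rule works only if non-responders can be in the set. Protocol 7.4.4.2.2 and SAP Table 3 attach no responder condition. All of this favours the 'or' reading, and I accept that it is the more plausible one. It does not rescue the bullet, because the 'or' reading still admits short-follow-up subjects by outcome.

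Three further points stand as limits. The size of the bias rests on quantities the documents do not give. SAP 3.12 sets no interim test, alpha or success rule, so the error rates above are nominal: they show what happens if the exact test against 40% is applied to the interim set. And this SAP version looks towards the final report, so the bullet may be carried-over text that no further table will use. That reduces the practical weight, but the earlier interim report leaves the question of its denominator open.

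**Conclusion.** The point holds, as a defect that should be fixed. The interim denominator for Globin Response depends on the outcome under either reading. If both conditions are required, the rate is 100% and carries no information. Under the more plausible 'or' reading it is biased upward whenever some subjects under 18 months have already responded and some with 18 months have not. The direction does not depend on the assumptions; the size does. At a true 40% with 36 infused, the expected rate is 41% to 54% and the nominal type I error 0.024 to 0.258 across the assumed splits and shares. The bias is zero if nobody is under 18 months.

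Only the interim Globin Response summary is affected. The final criterion ("the final analysis will be at least 24 out of 41 subjects achieving Globin Response") uses all Group C subjects in the TP and stands. Whether any reported interim figure was affected cannot be told from the documents.

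**What to change.** In the Globin Response bullet of SAP 3.12, delete the words that require the response to have been achieved, and add Group C to match Table 4. The bullet then includes Group C subjects in the TP with actual or potential follow-up of 18 months or more, as the transfusion bullet already does and as VOE-CR does in TPVOE. SAP 3.12 extends the same criteria to Groups A and B, so their interim summaries are corrected too. Leave the Month 24 bullet alone, since its responder denominator is intended.

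State which denominator was used in any interim Globin Response table already produced, and correct that table only if it followed the current wording.

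The cost is a one-line SAP correction and one check of existing output. Conduct, sample size and the final analysis do not change. The corrected interim figure may be less favourable than one computed under the present wording.

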3.13. Final Analysis

A final analysis will be performed when last subject has completed the Month 24 Visit as specified in the protocol or discontinued from the study.

3.14. Additional Data Review

Safety data are reviewed on an ongoing basis for signal detection, DMC meetings and supporting preparation of regulatory submission documents. Analyses of study data may also be performed for the purposes of internal data review, regulatory agency interactions, and updating the scientific community.

